4.5 Dose Modifications and/or Dose Interruptions

Dose modifications are permitted to manage drug-related toxicities and to improve treatment tolerability in order to maintain the patient on therapy and prolong exposure to study treatment.

Dose modifications in Cycle 1 and Cycle 2 are discouraged to maximize exposure to study treatment and increase the likelihood of achieving an objective response.

Dose reduction is not allowed within each 28-day cycle, but only between cycles.

The Medical Monitor will review with the Investigator any decision to reduce, interrupt, or permanently discontinue either of the two components of the study treatment (pracinostat/placebo or azacitidine).

If a dose modification is required, a dose reduction should be implemented first, as described in the tables below.

One pracinostat dose reduction is allowed as shown in table below:

Table 1: Pracinostat Dose Reduction

| Dose Level | Pracinostat/Placebo |
|---------------|--|
| Starting Dose | One 60 mg capsule/3 days per week/ 3 weeks in every 28-day cycle |
| Dose Level -1 | One 45 mg capsule/3 days per week/ 3 weeks in every 28-day cycle |

Up to two AZA dose reductions are allowed as shown in the table below:

Table 2: AZA Dose Reductions

| Dose Level | Azacitidine |
|---------------|--|
| Starting Dose | 75 mg/m ² for 7 days of each 28-day cycle |
| Dose Level -1 | 37.5 mg/m ² (50%) for 7 days of each 28-day cycle |
| Dose Level -2 | 25 mg/m ² (33%) for 7 days of each 28-day cycle |

Prior to dose reduction, the Investigator must assess if the toxicity is thought to be due to pracinostat, based on the safety information provided in the Investigator Brochure, or AZA, based on the safety information provided in the AZA product labeling. Severe fatigue, anorexia, weight loss, diarrhea, vomiting and QT prolongation are adverse reactions likely related to pracinostat, whereas pyrexia, injection site reaction, constipation and renal toxicity are adverse reactions likely related to AZA. Myelosuppression (i.e., thrombocytopenia, anemia, leukopenia, and neutropenia) has been reported with similar frequency with pracinostat and AZA therapy.

If toxicity is judged by the Investigator as likely related to pracinostat, then the pracinostat/placebo dose should be reduced first (Table 1). If the toxicity is judged by the Investigator as likely related to AZA, then the AZA dose should be reduced first (Table 2). If the Investigator is not able to ascertain the relationship of an adverse reaction to pracinostat or AZA, then dose reduction will begin with AZA, since AZA is administered to all patients whereas pracinostat is administered to only 50% of patients (i.e., those randomized to Group A). If azacitidine dose is reduced first, and it is determined that further dose modifications are still required after two AZA dose reductions, then pracinostat dose should be reduced.

Dose re-escalations are not allowed for either pracinostat or AZA after a dose reduction. If dose reduction is not sufficient to manage toxicity, then dose interruption of both pracinostat and azacitidine is permitted.

If study treatment is delayed due to toxicity, then the first day when treatment is resumed will be defined as Day 1. The subsequent cycles should return to 28 days in length.

4.5.1 Dose Modification or Interruption for Hematologic Toxicity

Dose modification for hematologic toxicity in the setting of AML is not allowed during the first cycle of treatment (Cycle 1) and not recommended in general, unless the patient is in remission as dose delays and/or reductions may decrease exposure to therapeutically effective levels of drugs.

[figure not shown]
Since myelosuppression (i.e., thrombocytopenia, anemia, leukopenia, and neutropenia) has been reported with similar frequency with pracinostat and AZA therapy, the AZA dose should be reduced first.

From cycle 2 onwards the following criteria are recommended:

- a) **Subjects with baseline ANC <1,500 cells/ μ L or platelets <75,000 cells/ μ L and have a \geq Grade 3 decrease in cell counts before starting next treatment cycle:**

 1. $\leq 50\%$ decrease: may continue treatment with no delay or dose adjustment.
 2. **>50% decrease and a bone marrow evaluation is not required per study protocol:** delay treatment. If recovery is achieved within 14 days, no dose adjustment is required. If recovery is not achieved within 14 days, at day 42 a bone marrow evaluation is suggested and dose adjustment is outlined in [Figure 2](#).
 3. **>50% decrease and a bone marrow evaluation is required per study protocol:** follow dose adjustment outlined in [Figure 2](#).

Figure 2: Dose Adjustment

*Recovery= count \geq nadir count + [0.5 x (baseline count – nadir count)]

b) **Subjects without reduced baseline counts (ANC \geq 1,500 cells/ μ L and platelets \geq 75,000 cells/ μ L) and have a \geq Grade 3 decrease in cell counts before starting next treatment cycle: delay treatment. If recovery is achieved within 14 days, no dose adjustment is required. If recovery is not achieved within 14 days the dose should be adjusted as follows:**

1. **ANC $>$ 1.000 cells/ μ L and PLT $>$ 50.000 cells/ μ L:** no dose adjustment is required;
2. **ANC \leq 1.000 cells/ μ L and/or PLT \leq 50.000 cells/ μ L:** consider reduction of AZA to dose level -1.

If it is determined that further dose modifications are still required after two AZA dose reductions, then pracinostat dose should be reduced. Unless a patient achieves $<$ 5% blasts in the bone marrow, a cycle should not be interrupted beyond 28 days due to hematologic toxicity.

Patients with drug interruptions for prolonged myelosuppression (defined as $>$ 56 days [2 cycles] with ANC $<$ 500/ mm^3 or platelet count $<$ 10.000/ mm^3 in a bone marrow with $<$

5% blasts and no evidence of disease or dysplasia), may only restart treatment after discussion with the Medical Monitor.

4.5.2 Dose Modification or Interruption for Non-Hematologic Toxicity

From Cycle 2 onwards in case of Grade ≥ 3 non-hematologic toxicities a dose reduction or, as subsequent option, a dose interruption of both pracinostat and azacitidine is permitted, after prior discussion with the Medical Monitor.

Patients with Grade ≥ 3 non-hematologic toxicities may have both pracinostat/placebo and azacitidine held up to a maximum of 4 weeks, or until return to Grade 1 or baseline (whichever comes first). However, in patients who are experiencing a reduction in marrow blasts but have not achieved counts $< 5\%$, dose interruptions beyond 28 days are permitted, but require prior discussion with the Medical Monitor.

- If unexplained reductions in serum bicarbonate levels (or carbon dioxide - CO₂- if bicarbonate is not routinely measured at the site) to < 20 mmol/L occur, then the AZA dose should be reduced by 50% for all subsequent cycles.
- If unexplained elevations of urea/BUN or serum creatinine to ≥ 2 -fold above baseline values and above ULN occur, then the next cycle should be delayed until values return to normal or baseline and the AZA dose should be reduced by 50% for all subsequent cycles.
- When a QT prolongation is observed for the first time, the patient should be followed with additional ECGs as determined by the Investigator. Both pracinostat/placebo and azacitidine should be held in patients who develop any of the following, unless there is a clear alternative cause for the changes:
 - Sustained (at least two ECG measurements, approximately 30 minutes apart) QTcF that is ≥ 500 ms and/or > 60 ms longer than the baseline value at screening
 - New ECG finding of clinical concern.

Study drug and azacitidine may be resumed when QTcF returns to baseline (i.e., 450 ms in case of absolute increase ≥ 500 ms or the patient's screening value $+30$ ms in case of increase > 60 ms), any other ECG abnormalities have been resolved, and underlying causes have been addressed, the patient remains clinically stable and is appropriately monitored. Clinical judgment should be applied.

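### For a patient already on reduced azacitidine, the 50% cut in Protocol 4.5.2 conflicts with Table 2 and its limit of two reductions

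*Protocol*

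**What the plan says.** Protocol 4.5 sets the general scheme. On azacitidine (AZA) it says "Up to two AZA dose reductions are allowed as shown in the table below", and Table 2 lists a start of 75 mg/m², level -1 at 37.5 mg/m² (labelled 50%) and level -2 at 25 mg/m² (labelled 33%). Re-escalation is barred. If more is needed after two AZA reductions, the section turns to the pracinostat dose.

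Protocol 4.5.2 gives two specific triggers. For an unexplained fall in bicarbonate (or CO₂) below 20 mmol/L, "the AZA dose should be reduced by 50% for all subsequent cycles". For an unexplained rise in urea/BUN or creatinine to at least twice baseline and above the upper limit of normal, the next cycle is delayed and the same 50% reduction applies. Neither bullet says what the 50% is a percentage of, or what to do if the patient has already been reduced.

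On the order of actions, Section 4.5 says "If a dose modification is required, a dose reduction should be implemented first" and allows interruption of both drugs if reduction is not enough. Section 4.5.1 handles hematologic toxicity by delaying first: "If recovery is achieved within 14 days, no dose adjustment is required".

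**The concern.** Two dosing instructions in one protocol give different answers for the same patient, and nothing says which prevails. The situation is foreseeable. Sections 4.5 and 4.5.1 make AZA the first drug to be reduced for myelosuppression and for toxicity of unclear cause, so a patient can be at 37.5 mg/m² before any renal or bicarbonate trigger. Renal impairment is itself a qualifying comorbidity (inclusion criterion 2.II.g), and Section 4.3.2.4 warns of higher renal risk in such patients. Because re-escalation is barred, whichever reading is taken applies for the rest of treatment.

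Three things are at stake:

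- **Patient safety and consistency.** AZA is the background therapy in both arms.
- **Deviation classification.** SAP 4.4 requires per-protocol patients to have received study drug and AZA without major deviations, and SAP 7.6 leaves the major/minor decision to the blind data review meeting. Conflicting text gives that meeting no fixed standard for this case.
- **Exposure reporting.** SAP 9.1 counts AZA reductions on the footing that two are possible. A dose of 18.75 or 12.5 mg/m² does not fit that count.

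**Working it through.** **Inputs.** Table 2 (Protocol 4.5): 75, 37.5 and 25 mg/m², at most two reductions. Protocol 4.5.2: a 50% reduction, reference dose not stated.

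**Table 2 reproduced.** The labels are percentages of the starting dose: 37.5 / 75 = 50.0% and 25 / 75 = 33.3%. The steps from the preceding level are 1 − 37.5/75 = 50.0% and 1 − 25/37.5 = 33.3%. Only the first step is a 50% cut.

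**The 50% rule applied at each level:**

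- *From 75 mg/m².* 0.5 × 75 = 37.5 on either reference dose, which is level -1. No conflict.
- *From 37.5 mg/m².* Half the current dose: 0.5 × 37.5 = 18.75 (25% of the start, not in Table 2). Half the starting dose: 0.5 × 75 = 37.5, so no change. Next level in Table 2: 25. Neither reading of the 50% reaches 25.
- *From 25 mg/m².* Half the current dose: 0.5 × 25 = 12.5 (16.7% of the start), a third reduction where two are allowed. Half the starting dose is 37.5, an increase that the re-escalation ban excludes. Table 2 has no further level.

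**Size at 37.5 mg/m².** The extremes differ by 37.5 / 18.75 = 2.0. Against level -2, 18.75 is 25 − 18.75 = 6.25 mg/m² lower, which is 6.25 / 25 = 25%. Over the seven doses of a cycle the three readings give 7 × 18.75 = 131.25, 7 × 25 = 175 and 7 × 37.5 = 262.5 mg/m².

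**Order of actions, side by side:**

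- Section 4.5: reduce; interrupt both drugs if that is not sufficient.
- Section 4.5.1: delay; no adjustment if counts recover within 14 days.
- Section 4.5.2, opening paragraph: reduction, with interruption as the subsequent option.
- Section 4.5.2, creatinine bullet: delay and reduce together.
- Section 4.5.2, QT bullet: hold both drugs, with no reduction step before it.

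The protocol does not define a delay as distinct from an interruption, so a reader cannot tell whether the delay and hold steps are exceptions to the general order or lie outside it.

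**The case against.** The best defence is that Table 2 governs. Its percentages refer to the starting dose, Section 4.5 says reductions follow the tables, and the cap is explicit. On that view 18.75 and 12.5 mg/m² arise only if the 50% is applied to the current dose and the table is disregarded, so what remains is a gap. Much of this is fair, but it does not settle the case: reading the 50% against the starting dose leaves a patient at 37.5 mg/m² where they are, although the bullet orders a reduction, and still does not give the table's 25. Nor does the protocol say whether the specific rule or the table takes precedence.

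The Medical Monitor reviews every decision to reduce or interrupt. That should lessen variation between sites, but it supplies no rule for choosing among the readings. Figure 2 is not available in the text reviewed; Section 4.5.1 cites it for hematologic adjustment, so it is not expected to settle the renal and bicarbonate rule.

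Two stronger readings are tempting and are not supported:

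- *That the Cycle 1 rules contradict each other.* Section 4.5 says "Dose modifications in Cycle 1 and Cycle 2 are discouraged", and Section 4.5.1 says that modification for hematologic toxicity "is not allowed during the first cycle of treatment". These read as a general rule and a stricter specific one, and a site that follows the stricter one breaks neither. Section 4.5 also bars dose reduction within any cycle.
- *That the reduce-first sentence flatly contradicts delaying first.* That sentence is conditional on a modification being required, and Section 4.5.1 can be read as deciding whether one is. Its criteria are recommendations, and Section 4.5 itself provides for delays. The tension lies instead in the later sentence of Section 4.5 on interruption, set against the delay and hold steps, and it is largely one of terminology.

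**Conclusion.** The conflict is real for a patient at 37.5 or 25 mg/m² who then meets the bicarbonate or urea/creatinine trigger. At 37.5 mg/m² three doses can be read from the text, spanning 18.75 to 37.5 mg/m²; at 25 mg/m² one reading breaks the two-reduction cap. The first reduction, from 75 mg/m², is consistent. The ordering of reduction, delay and interruption is a lesser matter of undefined terms.

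The documents do not say how many patients would be affected. It takes a prior AZA reduction followed by a specific laboratory trigger, so it is assumed to be uncommon.

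A reader might infer that the trial's main result is at risk. It is not. The primary analysis is overall survival in the ITT set, and alpha, power and the event target do not depend on these rules. The per-protocol analysis is secondary and, under SAP 13, may be dropped. The relative-dose measure in SAP 9.1 uses 75 mg/m² as its expected dose whatever reductions occur, so it would still record the dose given. The consequences are confined to patient safety, consistency of AZA dosing, and the standard for deviations and for counting reductions.

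**What to change.** Reconcile Protocol 4.5.2 with Table 2 for patients already at a reduced AZA dose. The text should state the reference dose for the 50%, how the instruction fits the limit of two reductions, and what applies to a patient at level -1 and at level -2. Then use reduction, delay, hold and interruption with one defined meaning each across Sections 4.5, 4.5.1 and 4.5.2, and state their order for each type of toxicity. Which dose or rule is right is for the sponsor's clinical team; this review proposes none.

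The deviation criteria applied at the blind data review meeting, and the count of AZA reductions in SAP 9.1, should follow the reconciled wording. The cost is a protocol clarification and a note to sites, with no change to design, sample size or primary analysis. It remains useful late in the study, because patients may continue treatment into the Post-Study Observation Period (Protocol 3.2 and 5.3).

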4.5.3 Dose Interruption in Patients with $< 5\%$ Bone Marrow Blasts (“Drug Holiday”)

A single dose interruption of study treatment for up to 1 cycle (28 days) is allowed but is not recommended in patients who request a “Drug Holiday” and meet all the following criteria:

- Received a minimum of 12 cycles of pracinostat/placebo + azacitidine
- Achieved BM blasts $< 5\%$ (i.e., CR, CRi or MLFS)
- Have been in clinical remission (CR, CRi, MLFS) for a minimum of 3 cycles

- If abnormal cytogenetics at baseline, have achieved a cytogenetic CR (CRc)

Both pracinostat/placebo AND AZA must be interrupted during this Drug Holiday. Also, no other treatments for AML, including another investigational product from a different research study, may be administered during this Drug Holiday. Patients who receive another treatment for AML during the Drug Holiday must be discontinued from the active phase of the study and will enter the Long-term Follow-up. Every effort should be made to complete the End of Study Treatment visit **prior** to the patient starting any AML treatment regimen other than pracinostat/placebo + AZA.

Prior to starting the “Drug Holiday”, the Drug Holiday Commencement visit (Section 5.1.13.1) must be completed. This study visit should occur on Day 1 of a cycle. For example, if the patient is at Cycle 18 Day 8, then the patient should complete the remaining study visits for that cycle, including study treatment administration (pracinostat/placebo + AZA).

To monitor patients for safety and potential disease progression during the Drug Holiday, study visits must be performed within 4 weeks (+/- 4 days) (Section 5.1.13.2).

When patients complete the Drug Holiday period, they will resume their randomized study treatment assignment, i.e., pracinostat/placebo + AZA. Patient may resume study treatment during the Drug Holiday period at any time after disease evaluation.

4.6 Management of Toxicity

Patient management, including transfusions, use of growth factors, prophylaxis and treatment of infections, will be performed according to institutional guidelines. Palliative and supportive care for disease related symptoms may be administered at the Investigator’s discretion and institutional guidelines.

4.6.1 Prophylactic Therapies

Patients should be pre-medicated for nausea and vomiting. Other prophylactic measures (i.e., anti-infectives) may be used as indicated.

4.7 Prior and Concomitant Medications

Information about prior and concomitant medication is to be collected from 28 days prior to Day 1 of Cycle 1 up to the End of treatment visit (Section 5.1.14) and recorded in the CRF.

Infusion of blood products is to be recorded. Particular attention should be paid to the collection of information regarding red blood cell and platelet transfusions: specifically date of transfusion, type of transfusion (red blood cells or platelets), and number of events (e.g., 2 units of red blood transfused at the same moment are considered as one transfusion event).

62

All medications administered in relation to diagnostic procedures, e.g., anesthetics and antibiotics are to be recorded.

Prophylactic infusion of saline solution prior to chemotherapy in order to prevent toxic reactions related to chemotherapy should be recorded as well.

4.7.1 Medications Affecting Metabolism of Pracinostat via Cytochrome P450

Few clinical information is available on drug interactions for pracinostat. Pracinostat is substrate of cytochrome P450 1A2 (CYP1A2), P450 2C8 (CYP2C8) and cytochrome P450 3A4 (CYP3A4). Caution in use of pracinostat is required with drugs that inhibit 3A4 and 2C8 or induce CYP1A2, 2C8 and 3A4 (see Investigator Brochure and study PRAN-17-14). Lists of 3A4 and 2C8 inhibitors and 1A2, 2C8 and 3A4 inducers are provided in [Appendix G](#).

Patients should avoid grapefruit juice and Seville oranges during the study since they are known to be inhibitors of CYP3A4.

Smoking results in CYP1A2 induction and has been shown to decrease pracinostat C_{max} and AUC by ~60%. This effect is known to be caused by substances created by tobacco smoke, such as polycyclic aromatic hydrocarbons (potent inducers of CYP1A2, a primary CYP450 isoform responsible for pracinostat metabolism). Therefore, current smokers are excluded from the study but the use of patches, chewing gums or vaping nicotine containing fluids is permitted. Patients who stopped smoking at least 8 days prior to first pracinostat dosing can be enrolled, provided they refrain from smoking during the entire study.

4.7.2 Possible Effects of Pracinostat on Other Drugs via Cytochrome P450

In hepatocytes pracinostat is an inducer of CYP1A2 and CYP2B6, while is a suppressor of CYP3A4 mRNA expression and enzymatic activity (see Investigator Brochure and PRAN-17-04).

Pracinostat should be used with caution in patients receiving concomitant medications that are primarily metabolized through CYP3A4. The plasma concentrations of CYP3A4 substrates can increase when co-administered with pracinostat. Lists of CYP3A4 substrates are provided in [Appendix H](#).

Pracinostat should be used with caution in patients receiving concomitant medications that are primarily metabolized through CYP1A2 and CYP2B6. The plasma concentrations and the efficacy of CYP1A2 and CYP2B6 substrates can decrease when co-administered with pracinostat. Lists of CYP1A2 and CYP2B6 substrates are provided in [Appendix H](#).

4.7.3 Prohibited Concomitant Medications

The following treatments and/or medications are prohibited while on study:

- Any other investigational product taken within 4 weeks prior to Day 1 of Cycle 1 and/or through the entire study treatment period is not allowed. For this purpose "Other investigational product" has to be intended as any agents tested in clinical trials, even those which are tested for indications that are already approved.

- Anticancer agents. If such agents are required, then the patient must discontinue study treatment prior to receiving the anti-cancer therapy and disease progression should be documented. For patients at Cycles 1 through 6, it is recommended to contact the Medical Monitor prior to study treatment discontinuation. Every effort should be made to complete the End of Study Treatment visit **prior** to the patient starting any AML treatment regimen other than pracinostat/placebo + AZA.
- Hydroxyurea is allowed until Cycle 1, Days 1-14, to reduce WBC count to <30,000 μ L prior to Day 1. After Cycle 1, Day 14, hydroxyurea is prohibited.
- HDAC inhibitors.
- Medications with a known risk of prolonging the QT interval and/or causing Torsades de Pointes. ([Appendix I](#)).
- Herbal products are not allowed throughout the study. Subjects should stop using these prior to the first dose of study treatment.

4.8 Treatment compliance

During each cycle a patient will be considered to be compliant with therapy if s/he takes at least 8 of the 9 capsules of study drug provided in the clinical study medication kit and at least 6 of the 7 AZA doses.

5 STUDY CONDUCT

This study will consist of three phases: Screening, Treatment, and Long-term Follow-up. During the treatment phase, there is a ± 4 -day window, while during the Long-term Follow-up there is a ± 1 -month window for the visits/calls.

5.1 Study Procedures

5.1.1 *Informed Consent*

Prior to performing any study-specific evaluation, written informed consent is to be obtained from each patient. The consent may be obtained at the earliest one week before the start of screening activities.

5.1.2 *Screening Assessments*

Screening examinations will only be performed after the patient has given written Informed Consent.

The following evaluations and procedures will be performed within 28 days prior to the first study treatment administration (Cycle 1 Day 1):

- Obtain demographic information: age, gender, and self-reported race/ethnicity
- Collect medical history, concomitant illnesses, prior surgeries, and smoking status: clinically significant diseases, prior cancer history, including cancer therapies and relevant procedures, should be collected
- Assess protocol-qualifying comorbidities. This may require measurement of the left ventricular ejection fraction (LVEF) and/or pulmonary function tests (ECHO/MUGA and/or pulmonary function tests are required to satisfy inclusion criteria IIb and IIc)
- Perform a complete physical examination (Section 6.2.1)
- Obtain vital signs (Section 6.2.2), including height, weight, blood pressure (sitting or in semi-supine position), pulse rate, and body temperature
- Assess ECOG performance status
- Obtain 12-lead ECG in triplicate (Section 6.2.3)
- Collect information about prior and concomitant medications (Section 4.7)
- Assessment of adverse events
- Collect adequate bone marrow aspirate/biopsy (Section 6.1.1)
 - Morphologic diagnosis of AML (a morphologic evaluation of bone marrow already performed within 30 days prior to the ICF signature will be accepted as screening evaluation)
 - Classical cytogenetic analysis - karyotyping (central evaluation) to assess cytogenetic risk category and allow stratification by cytogenetic risk factor (intermediate vs. unfavorable) at randomization and to evaluate cytogenetic response to therapy in patients with abnormal cytogenetics at baseline. If a bone marrow aspirate sample at screening has been already submitted for central cytogenetic analysis but the result is not available to confirm patient eligibility

and a local cytogenetic analysis (karyotyping) has been already performed as per clinical routine within 30 days prior to the ICF signature, the local result will be considered acceptable to enroll the patient. In case of discrepancy between the local and the central result of the baseline cytogenetic analysis leading to different cytogenetic risk categories, the patient should be randomized in the risk category defined by the central assessment. In case the central result should not be available, the local result will be used for randomization.

- Unknown cytogenetic risk results according to SWOG classification will be stratified as intermediate risk, as suggested by ELN 2017 classification.
- MRD panel determination
- If no bone marrow blood can be aspirated at screening (“dry tap”, even at repeated attempts) the patient will be considered a screen failure.
- Biobanking for mutational analysis (mandatory in all patients). Peripheral blood and bone marrow fluorescence in situ hybridization (FISH) analysis for cytogenetic study and molecular analysis are not required. However, if FISH testing or molecular analysis are part of the institution’s standard of care, the results will be recorded in the Case Report Forms.

The following evaluations and procedures will be performed **within 8 days prior** to the first study treatment administration (Cycle 1 Day 1):

- Laboratory assessments (Section 6.2.4)
- Serum pregnancy test for women of childbearing potential (Section 6.2.4)

Screening evaluations must be completed and patients must meet all eligibility criteria prior to randomization. Eligibility criteria, including the co-morbidities that define unfitness to receive intensive induction chemotherapy, must be reviewed and approved by the Medical Monitor prior to randomization.

Re-screening of a patient who has previously failed study entry will require appropriate discussion with the Medical Monitor and will be approved on a case by case basis.

If one or more screening laboratory tests do not support eligibility, laboratory re-test is permitted only once. Only the laboratory tests which resulted out of range need to be repeated.

In case of re-screening of a patient after one course of hypomethylating agent therapy, all the screening assessments need to be repeated, excluding cytogenetic test.

- Biomarker analysis (if consent obtained by patient): Peripheral blood samples and/or aspirate bone marrow samples will be collected and stored for potential molecular studies (Section 6.4)

5.1.3 Cycle 1 on Day 1

After confirmation of eligibility, the patient will be randomized to one of the two treatment groups using the IWRS. The following activities are to be performed **before study treatment administration**:

- Assess transfusions of red blood cells or platelets performed during the previous 8 weeks (Section 6.1.2).
- Perform a limited physical examination
- Measure blood pressure and pulse rate –**pre-dose** (sitting or in semi-supine position), body temperature, and weight
- 12-lead ECG measurement in triplicate - **pre-dose**
- Collect concomitant medications and any new medical conditions since the screening visit
- Assess ECOG performance status
- Administer the Quality of Life questionnaire
- Urine pregnancy test for women of childbearing potential – **pre-dose**
- Re-check of all eligibility criteria
- Assessment of adverse events
- Randomization via IWRS: The IWRS will provide the investigator with the kit number stored in the site stock to be dispensed to the patient.
- Treatment administration: The study treatment administration schedule is the following:
 - Pracinostat/placebo administration (see Section 4.2): according to the indication reported on the study kit internal panel, the patient will receive 1 capsule of study drug or matching placebo (week 1, day 1). Patient must begin study treatment within 24 hours after randomization.
 - Azacitidine administration: according to indication reported in Section 4.3.1.2 azacitidine is administered to patient.

Pracinostat/Placebo oral administration is to be taken before administration of azacitidine.

The date and the precise time (hh:mm) of the study drug and Azacitidine administration as well as other information related to the quantity and origin of the Azacitidine vials must be recorded in the source records as well as on the relevant eCRF page for each medication given. The relevant peel-off labels from the study kit and from the Azacitidine commercial packs used for the treatment at this visit will be attached to the drug accountability log (pharmacist or designated responsible).

Activities to be performed **after study drug administration (for all patients EXCEPT those participating in the AZA/pracinostat PK sub-study**. See Section 6.3):

- Collect three pharmacokinetic (PK) blood samples:
 - 30 minutes (\pm 15 minutes) **post** pracinostat/placebo administration
 - 3 hours (\pm 30 minutes) **post** pracinostat/placebo administration
 - 6 hours (\pm 30 minutes) **post** pracinostat/placebo administration

(IN SELECTED SITES ONLY) AZA/pracinostat PK sub-study: Assessment of the possible drug interaction of Pracinostat on the PK of Azacitidine (See Section 6.3.2):

- Collect 8 pharmacokinetic (PK) blood samples:
 - 15 minutes (\pm 2 minutes) **post** pracinostat/placebo and AZA administration
 - 30 minutes (\pm 2 minutes) **post** pracinostat/placebo and AZA administration
 - 1 hour (\pm 5 minutes) **post** pracinostat/placebo and AZA administration
 - 2 hours (\pm 5 minutes) **post** pracinostat/placebo and AZA administration
 - 3 hours (\pm 5 minutes) **post** pracinostat/placebo and AZA administration
 - 4 hours (\pm 5 minutes) **post** pracinostat/placebo and AZA administration
 - 6 hours (\pm 30 minutes) **post** pracinostat/placebo and AZA administration
 - 8 hours (\pm 30 minutes) **post** pracinostat/placebo and AZA administration (optional sampling)
- Triplicate ECGs will be done **90 minutes** (\pm 30 minutes) and 6 hours (\pm 30 minutes) **post** pracinostat/placebo administration.
- Measure blood pressure and pulse rate (sitting or in semi-supine position), **90 minutes** (\pm 30 minutes) **post** pracinostat/placebo administration.

5.1.4 Cycle 1 on Day 2

The following activities are to be performed on Day 2 of the first cycle:

- Collect one PK blood sample at 24 hours (\pm 1 hour) **after** the first pracinostat/placebo dose, **prior** to AZA administration (**for all patients EXCEPT those participating in the AZA/pracinostat PK sub-study. See Section 6.3**)
- Collect one PK blood sample at 24 hours (\pm 1 hour) after the first pracinostat/placebo dose, **prior** to AZA administration (**IN SELECTED SITES ONLY**) AZA/pracinostat PK sub-study (See Section 6.3.2)
- Triplicate ECGs will be done at **24 hours** (\pm 1 hour) **after the first** pracinostat/placebo administration, **prior** to AZA administration
- Administer the second AZA dose. Administration should be performed 24 hours (\pm 1 hour) after the first dose.
- Review concomitant medications since the previous study visit
- Assess AEs since the previous visit

5.1.5 Cycle 1 on Day 3

The following activities are to be performed on Day 3 of the first cycle:

- Collect one PK sample at 48 hours (\pm 2 hours) after the first pracinostat/placebo dose, **prior** to second pracinostat administration (for all patients, including those in the AZA PK sub-study)
- Pracinostat/placebo administration, 48 hours (\pm 2 hours) after first pracinostat/placebo dose and after PK sampling

- Triplicate ECGs will be done at **48 hours** (\pm 1 hour) **after the first** pracinostat/placebo administration, **prior** to AZA administration
- AZA administration (to be administered after PK sample collection)
- Review concomitant medications and therapies (in particular transfusions) since the last study visit
- Assess AEs since the previous visit
- Hand-out to the patient the study medication for the first cycle and give clear instructions regarding the intake (see Section 4.2.1.2).

